12.8 Allergic Reaction or Hypersensitivity to Components of VeraCept

If a subject experiences allergy-related symptoms or a hypersensitivity reaction (e.g., urticarial allergic skin reaction, rash) while VeraCept is placed, she should be assessed for a possible allergy to the components of VeraCept (nickel, titanium, and copper). A clinician will determine the historical relationship between symptoms and IUS use to inform a determination of causality. As needed, a nickel, titanium, and/or copper patch test will be performed and/or an assessment by a specialist for VeraCept users. If the IUS is determined to be the cause or highly suspected of causing the allergic reaction or hypersensitivity, the

IUS should be removed, and the AE(s) must be followed until resolution, the condition stabilizes, 30 days post study drug removal, or the subject dies or is lost to follow up (including withdrawal of consent/assent), whichever occurs first.

12.9 Discontinuation Visit

All subjects will be required to use an alternative contraceptive for the first 14 days following VeraCept removal, as described in Section 12.7.

12.9.1 Early Discontinuation due to an AE

If a subject requests VeraCept removal because of an AE, the Study Exit Visit (see Section 12.7) should be completed and documented on the CRF at the time of IUS removal. The subject will be followed until resolution of the event or 30 days after removal, whichever occurs first.

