8.1 Inclusion Criteria

Subjects must meet all of the following criteria to participate in this study:

- 1. Post-menarcheal, pre-menopausal females up to 45 years of age at the time of informed consent/assent and in good general health;
- 2. History of regular menstrual cycles defined as occurring every 21-35 days when not using hormones or prior to recent pregnancy or spontaneous or induced abortion;
- 3. Sexually active with a male partner who has not had a vasectomy;
- 4. Reasonably expect to have coitus at least once monthly during the study period;
- 5. In a mutually monogamous relationship of at least 3 months duration;
- 6. Seeking to avoid pregnancy for the duration of the study;
- 7. Willing to use the study drug as the sole form of contraception;
- 8. Willing to accept a risk of pregnancy;
- 9. Subjects must be in compliance with cervical cancer screening guidelines per the American Society for Colposcopy and Cervical Pathology (ASCCP) guidelines without evidence of disease. Subjects who are age 21-24 y/o, at time of informed consent, must have a normal Papanicolaou test (Pap), atypical squamous cells of undetermined significance (ASC-US), or low-grade squamous intraepithelial lesion (LSIL). Subjects who are 25 or older at the time of informed consent with ASC-US results, must also have a negative high-risk human papilloma virus (HPV) test result within the appropriate screen timeframe, and prior to study IUS insertion. Alternatively, the subject must have had a colposcopy performed within the appropriate screen timeframe per American Society for Colposcopy and Cervical Pathology (ASCCP) guidelines, and prior to study IUS insertion that showed no evidence of dysplasia requiring treatment per ASCCP guidelines, or treatment was performed and follow-up at least 6 months after the treatment showed no evidence of disease by clinical evaluation;
- 10. Able and willing to comply with all study tests, procedures, assessment tools (including e-diary), and follow-up;
- 11. Able and willing to provide and document informed consent and Authorization for Release of Protected Health Information (PHI). Unemancipated subjects under 18 years old must provide assent and have written parental consent documented on the consent form consistent with local legal requirements;
- 12. Plan to reside within a reasonable driving distance of a research site for the duration of the study;
- 13. Subject agrees not to self-remove VeraCept;

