- 9. Contact subject (e.g., via phone, email, etc.). Starting at Week 17 from day of VeraCept insertion.
- 10. See Appendix 2 for the IUD Insertion Subject Numeric Pain Rating Scale
- 11. See Appendix 3 for the IUD Removal Subject Numeric Pain Rating Scale
- 12. Upon receipt of informed consent and assent, if applicable, contact the IWRS to register the subject, initiate the subject's screening diary and obtain a subject number
- 13. Contact the IWRS prior to insertion to obtain an enrollment number, the IUS dispensation assignment, and initiate the enrollment diary. If an IUS insertion is a failure, contact the IWRS to record the IUS insertion failure and to obtain a second IUS dispensation assignment or to discontinue the subject
- 14. See Appendix 4 for Pre-Removal Planning Timing
- 15. See Appendix 5 for Removal Instructions
- 16. An additional contact will be performed 30 days post-removal or expulsion for any AEs that were ongoing at the time of VeraCept removal. If the date of expulsion is unknown the additional contact will be performed 30 days after the date of expulsion discovery.
- 17. Subjects completing at least 6 years (72 months) of study will complete a Subject Satisfaction Survey at the Exit Visit.

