 - If the subject elects to use hormonal contraceptive pills, a one-month supply of hormonal contraceptive pills will be provided to the subject by the site for the first 14 days following VeraCept removal
 - All subjects must be provided with a 14-day supply of condoms at time of removal (unless a new IUS is inserted)
 - All subjects must be instructed to continue use of new contraception method for 14 days after removal.
- Subjects should be reminded to avoid conception within 7 days after VeraCept removal
- Contact the IWRS to update the subject status
- Urine pregnancy test will be done 17 days after removal/study exit by the subject at home, with a required follow up call by the study coordinator or PI to obtain and document results
- An additional contact will be completed 30 days after VeraCept removal for any Adverse Events that remain ongoing at the time of IUS removal or expulsion. If the date of the expulsion is unknown the additional contact will occur 30 days after the date of expulsion discovery. AE stop date and outcome are required to be updated, if applicable.

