15.4 Causality: Serious Adverse Event and Adverse Event Relationship to Study Treatment

An Investigator who is qualified in medicine must make the determination of relationship to the drug for each AE. The relationship of an AE to the drug should be assessed using the guidelines presented in Table 2. An AE for which there has been no causal relationship reported initially will require follow-up to determine causality. Of the definitions in Table 2, "possibly", "probably" and "related" to an investigational medical product are considered adverse reactions. "Unlikely" and "not related" do not qualify as a causal relationship.

Table 2: Adverse Event Relationship to Drug

| Relationship to Drug | Description | |
|-------------------------|--|--|
| Related | Previously known toxicity of agent; or an event that follows a reasonable temporal sequence from administration of the drug; that follows a known or expected response pattern to the suspected drug; that is confirmed by stopping or reducing the dosage of the drug; and that is not explained by any other reasonable hypothesis | |
| Probably related | related The adverse event: | |
| | • Follows a reasonable temporal sequence from the time of study drug administration; and/or | |
| | Follows a known response pattern to the study drug; and | |
| | Was unlikely to have been produced by other factors such as the subject's clinical state, therapeutic intervention, or concomitant therapy | |
| Possibly related | The adverse event: | |
| | • Follows a reasonable temporal sequence from the time of study drug administration; and/or | |
| | Follows a known response pattern to the study drug; but | |
| | Could have been produced by other factors such as the subject's clinical state, therapeutic intervention, or concomitant therapy | |
| Unlikely related | The adverse event: | |
| • | • Does not follow a reasonable temporal sequence from the time of study drug administration; and | |
| | Was likely produced by other factors such as the subject's clinical state, therapeutic intervention, or concomitant therapy but for which relationship cannot be definitely ruled out | |
| Not related | The adverse event can be determined with certainty to have no relationship to the study drug | |

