15.6 Adverse Event Outcome

The investigator will categorize the outcome of each SAE and AE according to the definitions below:

Resolved: The subject recovered from the SAE or AE.

Resolved with sequelae: a condition whereby the consequences of a disease or injury include lingering effects.

Not Recovered/Not Resolved: At the time of the last assessment, the event is ongoing. Note: Ongoing SAEs and AEs are not considered resolved as a result of death and no SAE or AE stop date should be recorded for an AE that is ongoing at the time of death.

Fatal: Adverse Event directly caused death. The sponsor may request that the investigator perform or arrange for the conduct of supplemental measurements and/or evaluations. If a subject dies during participation in the study or during a recognized follow-up period, the sponsor should be provided with a copy of any post-mortem findings, including histopathology. Note: Death is an outcome of an adverse event and not an adverse event in itself. All reports of subject death should include an adverse event term (other than "Death") for the cause of the death.

Unknown: The Adverse Event outcome is unknown due to the subject becoming lost to follow-up or the subject withdraws consent and is unwilling to provide outcome

information. The outcome of "Unknown" should not be used if the subject is still active in study and/or is willing to provide outcome information.

Since reporting of an SAE is required within 24 hours of discovery, Death can be reported as an initial event term and updated to the final diagnosis in a follow-up report. If an adverse event term is not provided, the investigator will be queried to obtain the cause of death. Only in the rare occurrence that no verbatim description of an adverse event can be obtained from the investigative site will "Death – Unknown Cause" be used as the event term.

The investigator should attempt to establish a diagnosis of the event based on the signs, symptoms and/or other clinical information. In such cases, the diagnosis should be documented as the AE (and SAE if serious) and not the individual signs/symptoms.

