15.10 Follow-up of Adverse Events and Serious Adverse Events

All AEs and SAEs must be followed until resolution, the condition stabilizes, 30 days post study drug removal or expulsion, or the subject dies or is lost to follow-up (including withdrawal of consent/assent), whichever occurs first. The investigator is responsible for

ensuring that follow-up includes any supplemental investigations as may be indicated to elucidate as completely as practical the nature and/or causality of the AE/SAE. This may include additional laboratory tests or investigations, histopathologic examinations, or consultation with other health care professionals. Follow-up information should be submitted to the sponsor in a timely many as the information is obtained.

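### Follow-up of an SAE, pelvic infection or uterine perforation still open at removal or expulsion can end at Day 30 although the event is neither resolved nor stable

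*Protocol*

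**What the plan says.** Three places in the Protocol set the end of follow-up for an event that is ongoing when the device comes out.

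- Section 12.9.1, removal requested because of an AE: "The subject will be followed until resolution of the event or 30 days after removal, whichever occurs first".
- Section 15.10, the general rule: "All AEs and SAEs must be followed until resolution, the condition stabilizes, 30 days post study drug removal or expulsion", or death or loss to follow-up, whichever is first.
- Section 12.8, allergic or hypersensitivity reactions: the same list as 15.10, counted from removal.

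The schedule supports this with a single contact. Table 1, footnote 16: "An additional contact will be performed 30 days post-removal or expulsion for any AEs that were ongoing at the time of VeraCept removal". At that contact, according to section 12.7, "AE stop date and outcome are required to be updated, if applicable". Section 15.6 defines the outcome of an event that is still open: "Not Recovered/Not Resolved: At the time of the last assessment, the event is ongoing".

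Section 15.12 obliges the investigator to notify the sponsor of an SAE learned of at any time after removal if it seems reasonably related. Sections 2 and 18 follow exposed pregnancies through delivery and at least 6 weeks beyond.

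SAP section 4.1.11 imputes the stop date of a continuing event as the last known date on the study. SAP section 4.12.4 lists each AE with its cessation time, duration and outcome.

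**The concern.** When the earliest of several endpoints ends follow-up, the 30-day term is a ceiling. It has effect only in the cases that matter most: events that on Day 30 have neither resolved nor stabilised. The rule makes no distinction between a mild complaint and an SAE.

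The Protocol itself explains why some of these events deserve a known outcome. Section 6.2 says that pelvic infection can lead to tubal damage, hysterectomy, sepsis and rarely death, and that perforation may require laparoscopy or laparotomy. Section 15.3 makes both of them events of special interest. Safety is a secondary objective, and a safety narrative that stops at an arbitrary day while the event is active is weaker evidence than one that reaches an outcome.

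**Working it through.** The plan states no figure to reproduce. The check is a reading of the passages together, plus a short calculation for the listed duration.

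**Step 1. Does Day 30 close an active event?**

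| Section | Applies to | Resolution | Stabilisation | 30 days | Death or loss |
|---|---|---|---|---|---|
| 12.8 | allergic reactions, after removal | yes | yes | yes | yes |
| 12.9.1 | removal requested because of an AE | yes | not listed | yes | not listed |
| 15.10 | all AEs and SAEs, after removal or expulsion | yes | yes | yes | yes |

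All three use the first to occur. For a woman who is alive, in contact, not resolved and not stable, the only term left is 30 days, so the answer is yes. The table also shows that 12.9.1 does not match the other two.

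**Step 2. Does another passage keep an open SAE under follow-up?**

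- Section 15.12 is a duty to notify if the investigator happens to learn of a related SAE. It sets no follow-up of one that is already open.
- Sections 2 and 18 extend follow-up for pregnancies only.
- Section 12.9.2 keeps women who want to conceive in contact for up to 1 year, but to record conception, not AE outcome.

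No passage does so.

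**Step 3. What reaches the AE listing?** Let an event begin *a* days before removal and truly resolve *R* days after it. Let the last known date on the study be *K* days after removal. I assume that the listing uses the imputed stop date and counts duration as stop minus start plus one.

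- True duration = a + R + 1
- Listed duration = a + K + 1
- Shortfall = R − K

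If the last contact is the one at Day 30, K = 30 and the shortfall is R − 30 days, which is positive whenever R > 30. If that contact fails and the 17-day pregnancy-test call was the last one, the shortfall is R − 17. In a woman who stays in fertility follow-up, K can exceed 30 and the listed duration could even be too long. In each case the listed value reflects when contact ended, not when the event ended.

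**Step 4. How many events?** The documents give no resolution times, so the number of SAEs unresolved at Day 30 cannot be computed. Two figures give an outer scale for any occurrence, open or not, if earlier rates carry over.

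- Phase 2 reported SAEs in 10 subjects over 36 months (Protocol 1.1.3). Taking the 283 women with a placed device as denominator, 10/283 = 3.5%, and 0.035 × 1,605 ≈ 57.
- Section 6.2 puts pelvic infection and perforation among events seen in under 2% of pooled subjects. Since 0.02 × 1,605 = 32.1, that is at most about 32 women for each.

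Only the part that is open at removal and still active at Day 30 is affected. Use to 8 years could raise the base.

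**The case against.** The strongest defence is that the 30-day limit is deliberate. It appears consistently in several sections, it has a scheduled contact behind it, and many events will have resolved or stabilised by then. The clock starts only at removal or expulsion, so a perforated device still in place has not started it. Not Recovered/Not Resolved is a defined and visible outcome. A later sepsis or hysterectomy with hospitalisation would be an SAE, to be notified under section 15.12 if it seems related and the investigator learns of it. The SAP's AE summaries (4.12.1 and 4.12.2) tabulate neither outcome nor duration; these appear only in the listing. Late infertility after pelvic infection would also escape follow-up that ends at resolution or stabilisation.

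Most of this stands, and it limits the size of the point. It does not answer it: section 15.12 depends on the investigator happening to hear, and a visible open outcome is still an unknown one.

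A reader might go further in three ways that the documents do not support.

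- *Menstrual AEs closed before one menses has been seen.* Entry allows "History of regular menstrual cycles defined as occurring every 21-35 days when not using hormones", so 30 days is shorter than part of the range. With removal on a random cycle day and a 5-day menses, the share without a completed menses by Day 30 is (28 − 25)/28 = 11% for a 28-day cycle, (35 − 25)/35 = 29% for 35 days, and none at 25 days or less. Both premises are assumptions. Section 4.6.1 requires timing guidelines to be considered before removal, and pills or a new IUS at removal (12.7) may alter the first bleed. Section 6.2 is alphabetical, so it does not show that menstrual events are the main ones. Confirmation on stopping is mentioned in Table 2 only under Related, and SAP 4.1.10.4 pools possibly, probably and related.
- *A failed clock after a late-discovered expulsion.* Section 12.7 says: "If the date of the expulsion is unknown the additional contact will occur 30 days after the date of expulsion discovery". For a known date that the site learns of late, the contact date may have passed. However, section 12.9.3 still calls for an Exit Visit, which includes AE assessment, so little is lost.
- *A large affected group.* Phase 2 had 51/283 discontinuations for AEs. That count covers all AEs, not SAEs unresolved at Day 30, and should not be scaled up for this purpose.

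**Conclusion.** The point holds in a limited form. As written, the Protocol allows follow-up of an SAE, pelvic infection or uterine perforation to end 30 days after removal or expulsion while the event is still active, and nothing else requires it to continue. The consequence is an outcome left open and, on the assumption that listings use imputed stop dates, a listed duration that can be too short. This is a possibility for a small, uncounted set of events, not the usual course. It concerns ascertainment of safety outcomes only; the Pearl Index, the sample size and the planned AE incidence tables do not change. The point rests on the text and on no assumption about menses, cycle length or removal timing. It is worth acting on because the remedy is cheap.

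**What to change.** Put one sentence, identical in Protocol sections 12.8, 12.9.1 and 15.10, to this effect: SAEs, and pelvic infection or uterine perforation whether or not serious, that are ongoing at removal or expulsion are followed by remote contact until resolution, stabilisation, death or loss to follow-up, without the 30-day limit; other AEs keep the 30-day contact. Using the same sentence in all three places also settles whether stabilisation ends follow-up under 12.9.1.

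The extension should name pelvic infection and perforation rather than all events of special interest. That list also includes dysmenorrhea, abdominal pain and insertion pain, and open-ended follow-up of those would cost far more for little gain. The menstrual rules and the expulsion clock can stay as they are.

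The cost is Protocol wording, a few extra phone or email contacts, and a few AE records that close later. No visit or procedure is added, and the change affects data collection, not treatment. Section 12.9.2 already uses remote contact for up to a year in women seeking pregnancy, so the means exist.

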12.9.2 Early Discontinuation for Subjects who want to Attempt Pregnancy

If a subject requests VeraCept removal to become pregnant, the Study Exit Visit (Section 12.7) should be completed and documented on the CRF at the time of VeraCept removal. Subjects should avoid pregnancy within the 7 days post IUD removal. Additionally, subjects will be followed for either: 1 year or until they decide to no longer try to conceive or they become pregnant, whichever comes first. Outcome data regarding the subject's ability to conceive, or the decision to no longer try to become pregnant will be collected by contacting the subject (e.g., via phone, email, etc.) and documented in the source document and eCRF.

12.9.3 Early Discontinuation due to IUS Expulsion

Subjects exiting the study due to IUS expulsion should have a Study Exit Visit (Section 12.7), which should be completed and documented on the CRF. See Section 12.11 for instructions for pregnancy mitigation.

12.10 Unscheduled Visits

Unscheduled visits will be documented in the source and the CRFs. Medical evaluations will be conducted as indicated by the reason for the unscheduled visit.

12.11 IUS Expulsion

If the subject suspects the IUS has been expelled, she should contact the study site immediately. The subject should be scheduled for a visit as soon as possible and counseled to refrain from having sex or use appropriate non-hormonal contraception. Emergency contraception may be administered (e.g., ella® (preferred) or Plan B One-Step® based on provider and participant counseling and choice), according to product labelling, if the subject suspects that expulsion has occurred, and an act of intercourse might be unprotected, and she does not want the risk of pregnancy. A transvaginal ultrasound should be performed to confirm IUS presence and appropriate position, if clinically indicated. If the IUS is expelled, the subject will be exited from the study. The expulsion should be recorded as an AE on the CRF.

12.12 Missed Visits and Lost to Follow-Up

12.12.1 Missed Visits

All reasonable efforts should be made to ensure that enrolled subjects return to the investigational site for all study visits. Any subject who misses a scheduled visit or monthly contact follow-up should have contact attempts by the study staff as follows:

- At least three documented attempts to contact the subject (e.g., via phone, text, email, mail, etc.). Method of contact attempts should vary.
- If the subject cannot be contacted or is contacted and still fails to come in for a scheduled visit, a follow-up letter must be sent via email AND certified letter (unless a previous certified letter was returned as undeliverable).

Attempts to contact the subject should continue as described above for each missed visit. A visit is considered missed once the following visit window opens. The missed visit should be recorded as "visit not done" in the EDC.

12.12.2 Lost to Follow-Up

A lost to follow-up subject is a subject who does not come in for an exit visit/VeraCept removal at the time of study completion and their final status outcome is unknown. Study completion is defined as Month 60 (Year 5) for subjects who did not consent to the extension study and Month 96 (Year 8) for those who did consent to the extension study.

Subjects not returning for an exit visit but who provide a final status are not considered lost to follow-up (e.g., device removed by outside provider, withdrew consent, refused VeraCept removal, etc.). Every effort should be made to retrieve VeraCept for final study drug disposition.

Subjects previously designated as lost to follow-up under the prior lost to follow-up guidance (protocol Amendment version 6.0 or earlier) will be required to be contacted annually until the visit window for Month 60 (Year 5) has closed. Refer to Study Reference Manual for additional instructions.

Subjects discontinued as lost to follow-up who later resume contact with the site should be requested to come in for device removal or confirmation of removal and with a request to return VeraCept, if possible (see CCGs for instructions on updating the CRFs).

